1. PROTOCOL SYNOPSIS

This document is a protocol for a human research study. This study is to be conducted according to US and international standards of Good Clinical Practice (FDA Title 21 part 312 and International Conference on Harmonization guidelines), applicable government regulations and Columbia University Medical Center institutional research policies and procedures.

Title	A phase Ib high-throughout pancreas precision oncology study investigating the feasibility, efficacy, and pharmacodynamics of cell regulatory-network analysis based therapy selection in advanced pancreatic adenocarcinoma: HIPPOCRATES Part 2.		
Short Title	RNA precision oncology in advanced pancreatic cancer (HIPPOCRATES Part 2)		
Phase	Ib		
Methodology	This is a single arm, open-label phase Ib trial of FDA-approved or investigational agents in patients with locally advanced, unresectable or metastatic pancreatic cancer who have progressed on one or two prior lines of treatment to evaluate feasibility, safety, and efficacy of the OncoTreat algorithm.		
Study Duration	We estimate that the trial (Parts 1 and 2) will require up to 36 months to complete15 to 18 months for tissue acquisition on Part 1 (AAAR6703) and an additional 15-18 for treatment and follow-up to evaluate the efficacy outcomes for all subjects.		
Study Center(s)	Columbia University Irving Medical Center		

	1. Co-Primary objectives :
	 To evaluate the overall feasibility of using the OncoTreat technology to inform rational selection of off-label FDA-approved or investigational drugs in subjects with advanced pancreatic cancer (PDA) who have progressed on one or two prior lines of therapy. This will include the percentage of subjects who begin an OncoTreat-prioritized agent, defined as having received a single dose of study drug, and the "match rate," defined as the fraction of subjects who match with at least one OncoTreat-prioritized agent (p-value < 1 x 10⁻⁵). To evaluate the clinical efficacy of OncoTreat by assessing the objective response rate (ORR) for subjects treated with OncoTreat-prioritized drugs according to Response Evaluation Criteria in Solid Tumors (RECIST) v1.1 criteria.
Objectives	 The secondary objectives of this study are to: To describe the safety and tolerability, defined as the incidence of Grade 3/4 adverse events (AEs) in terms categorized and graded according to the National Cancer Institute Terminology Criteria for Adverse Events (NCI CTCAE v4.0), of using OncoTreat to inform rational treatment decisions in subjects with advanced PDA. The incidence of dose modifications, interruptions, and discontinuations will also be described. To assess the efficacy of OncoTreat by estimating the disease control rate (DCR) at 16 and 24 weeks, the median progression-free survival (PFS), the overall survival (OS), and the CA 19-9 tumor marker response. Assess the pharmacokinetics of each OncoTreat-prioritized agent in subjects with advanced PDA.
	 3. The exploratory objectives of this study are to: Explore the relationship between drug exposure, pharmacodynamics, efficacy, and safety of each OncoTreat-prioritized agent. Pharmacodynamic response will be evaluated by comparing the master regulator signature of a given subject's tumor using

	VIPER analysis, comparing pre-treatment and on-
	treatment tumor samples. The changes in master
	regulator activity between these two samples will be
	compared to that predicted from cell-based and PDX-
	based treatment studies.
•	Assess whether the master regulator signature, using
	VIPER analysis, in a given subject's tumor changes in
	response to standard-of-care treatment by comparing
	initial and secondary biopsies collected for each subject
	before and after one or two lines of systemic therapy
	(chemotherapy or clinical trial). These data will be used
	to determine whether the predicted sensitivity of a
	patient's tumor to the first- or second-line therapy that
	they receive is predictive of the actual clinical outcomes
	that are observed during treatment.
•	Using the same data as in the bullet point above, assess
	the frequency with which chemotherapy treatments alter
	the predicted sensitivity of tumors to other OncoTreat-
	prioritized agents (p-value $< 1 \ge 10^{-5}$).
•	Compare the standard-of-care clinical DNA mutation
	analysis results with matched master regulator activity
	profiles to correlate any clinically actionable genomic
	information with the top OncoTreat-prioritized drugs (p-
	value $< 1 \times 10^{-5}$).
•	Evaluate the feasibility of using the OncoTreat
	technology on peripheral blood circulating tumor cells
	(CTCs) by comparing master regulators generated from
	CTCs to those obtained from tumor tissue in matched
	pre- and on-treatment samples with an OncoTreat-
	informed agent.
•	Identify associations between master regulator profiles
	and additional clinical, epidemiological, physiological,
	imaging, or molecular features of the subject or subject's
	tumor.
•	Identify potential biomarkers, beyond the master
	regulator signature, using additional genomic, RNA,
	protein, and imaging platforms that are predictive or

	prognostic of response to each OncoTreat-prioritized agent.
Number of Subjects	We will enroll 30 subjects in Part 1 (AAAR6703) of the study to obtain detailed predicted therapy options. We anticipate accrual over 15-18 months. We estimate that 15 subjects will progress to Part 2, requiring an additional 15-18 months to complete treatment and for follow-up.
Diagnosis and Main Inclusion Criteria	Locally advanced, unresectable or metastatic pancreatic cancer who progressed on one or two prior lines of chemotherapy, for whom a precision therapy was recommended in Part 1.
Duration of administration	Treatment will continue until progressive disease, unacceptable adverse events, intercurrent illness that prevents further administration of treatment, investigator's decision to withdraw the subject, subject withdrawal of consent, pregnancy of the subject, noncompliance with trial treatment or procedure requirements, or administrative reasons requiring cessation of treatment.
Reference therapy	Not applicable – single arm study.

This is a single arm, phase Ib study with 2 co-primary endpoints: 1. Feasibility Endpoint: We will determine the feasibility of the OncoTreat platform in guiding therapy. The primary feasibility endpoint is whether a subject begins treatment on Part 2 based on results generated from the OncoTreat analysis. Previous attempts to match subjects based on DNA profiling yielded enrollment rates of 3-5%. We hypothesize that we will validate OncoTreat matches for 50% of subjects and that at least 30% of enrolled subjects (60% of matches) will begin therapy. With 30 enrolled patients we will have 84% power to detect a treatment rate of 30% compared to a historical treatment rate of 5% with alpha of 0.05. We will assess the "match rate" – the fraction of patients who match with at least one drug. With 30 enrolled patients, we will have 90% power with alpha = 0.05 to detect a 50% match rate (15 of 30) subjects) compared to a (liberal) estimated match rate of 20% based on DNA profiling in pancreatic cancer. 2. Clinical Endpoint: The primary clinical efficacy endpoint is the objective response rate for OncoTreat-prioritized drugs according to RECIST v1.1. The phase III trial (NAPOLI-1) that resulted in the FDAapproval of nanoliposomal irinotecan and 5-fluorouracil in the second-Statistical line setting demonstrated a median OS of 6.1 months versus 4.2 months Methodology for 5-fluorouracil monotherapy (primary endpoint), mPFS of 3.1 months, and an ORR of 16% (compared to 1% in the 5-fluorouracil arm). Thus, based on historical controls, the ORR for treatment-resistant metastatic PDAC is expected to be no more than 16%. Using the above mentioned rates, a sample size of n = 9 achieves at least a 80% power to detect a difference of 25% in ORR (30% vs 5%) using a one-sided binomial test with a target alpha of 0.1. To be conservative, we use the minimum number of patients (9) expected to be treated in this calculation. If at the end of the study the total number of objective responses is greater than or equal to 2, we will be able to reject the historical rate of 5% at the significance level of 0.05 with power of 69% and OncoTreat will have demonstrated a clear signal of clinically meaningful improvement in the primary endpoint for patients with advanced, previously-treated PDA. Assuming about 30% of enrolled patients will receive an OncoTreat-informed treatment, N = 30subjects is an appropriate sample size for this prospective study. Secondary measures include DCR, PFS, and OS as well as safety and tolerability of OncoTreat-directed therapy. The pharmacokinetics of OncoTreat-prioritized drugs in PDA subjects will also be described.

1.1 Trial Design Overview

This is a phase 1b, single-arm, single-center, open-label clinical trial for 30 evaluable patients with locally advanced or metastatic pancreatic cancer (PDA). Subjects with newly diagnosed locally advanced or metastatic PDA will be enrolled on protocol Part 1 (AAAR6703) prior to tumor biopsy. OncoTreat analysis will be conducted using a New York State CLIA-certified test. Subjects will receive physician's choice first-line cytotoxic chemotherapy (including 5-FU, gemcitabine, or capecitabine-based combinations or monotherapy) or clinical trial while preclinical validations of OncoTreat candidate treatments are performed. Preclinical results will be evaluated by the Precision Medicine Tumor Board (PMTB), which will review the data and prioritize a treatment based on the following criteria: 1) patient safety; 2) preclinical efficacy; 3) pharmacological properties; and 4) drug availability. If an agent is not identified or available at first progression, patients will continue on to second-line therapy (chemotherapy or clinical trial) and will be again assessed at the time of second progression. If an agent is identified and available, subjects will be enrolled on this protocol (Part 2), undergo a repeat biopsy and be treated on a single-arm, single-agent phase Ib clinical trial evaluating pharmacokinetics, safety, and efficacy in recurrent PDA patients.

This study will be conducted in conformance with Good Clinical Practices.

Specific procedures to be performed during the trial, as well as their prescribed times nad associated visit windows, are outlined in the Trial Flow Chart – Section 9.

1.2 Trial Schema

Figure 1. Phase Ib Trial Schema.

2. STUDY OBJECTIVES AND ENDPOINTS

2.1 Primary Objectives & Endpoints

2.1.1 Objectives:

The co-primary objectives of this study are:

- To evaluate the overall feasibility of using the OncoTreat technology to inform rational selection of off-label FDA-approved or investigational drugs in subjects with advanced pancreatic cancer (PDA) who have progressed on one or two prior lines of systemic therapy. This will include the percentage of subjects who begin an OncoTreat-prioritized agent, defined as having received a single dose of study drug, and the "match rate," defined as the fraction of subjects who match with at least one OncoTreat-prioritized agent (p-value < 1 x 10⁻⁵).
- To evaluate the clinical efficacy of OncoTreat by assessing the objective response rate (ORR) for subjects with advanced PDA treated with OncoTreat-prioritized drugs after disease progression on one or two prior lines of systemic therapy according to Response Evaluation Criteria in Solid Tumors (RECIST) v1.1 criteria.
- 2.1.2 Endpoints:

The co-primary endpoints of interest are:

- The percentage of subjects who begin an OncoTreat-prioritized agent, defined as having received a single dose of study drug, and the "match rate," defined as the fraction of subjects who match with at least one OncoTreat-priotitized agent (p-value $< 1 \ge 10^{-5}$).
- ORR according to RECIST v1.1 criteria.

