Step 4. Candidate drug selection. By integrating the above datasets, we can identify drugs that shut down the activity of the specific MRs active in an individual patient's profile. This analysis is integrated across the top 50 MRs for each patient. Successful matches are those drugs that reverse the activity of many or all of these top 50 MRs.

We have performed a preliminary analysis of the OncoTreat methodology on existing pancreatic cancer tumor profiles and found at least one matching drug for 85% of patients (using a conservative threshold FDR of 1×10^{-5}). Moreover, at least 50% of patients have 5 or more matched drugs using the OncoTreat approach, providing an opportunity to screen multiple candidate agents for a given patient using patient-derived models such as PDXs and organoids.

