12. STATISTICAL CONSIDERATIONS

This is a single arm, phase Ib study with 2 co-primary endpoints:

- Feasibility: The primary objective of this trial is to determine the feasibility of the OncoTreat platform in guiding therapy. The primary outcome is whether a subject begins therapy on Part 2. Previous attempts to match subjects based on DNA profiling have yielded enrollment rates of 3-5% [14, 78]. We hypothesize that we will validate OncoTreat matches for 50% of subjects and that at least 30% of enrolled subjects (60% of matches) will begin therapy on Part 2. With 30 enrolled patients on Part 1, we will have 80% power to detect a treatment rate of 30% on Part 2 compared to a historical treatment rate of 5% with alpha of 0.05. We will also assess the "match rate" the fraction of patients who match with at leaset one drug. With 30 enrolled subjects, we will have 97% power with alpha = 0.05 to detect a 50% match rate (15 of 30 subjects) compared to a (liberal) estimated match rate of 20% based on DNA profiling in PDA.
- Efficacy: The primary clinical efficacy endpoint is the **objective response rate (ORR)** for OncoTreat-prioritized drugs, which corresponds to the number of patients whose tumors demonstrate a 30% or greater reduction from baseline in the sum of the diameters of all target lesions amongst all evaluable patients, as assessed by standard-of-care CT scans. We target estimating the ORR and the corresponding 95% confidence interval.

Secondary endpoints will include: 1) **disease control rate (DCR) at 16 and 24 weeks**, which corresponds to the number of patients whose tumors demonstrate either an objective response or stable disease, defined as a no more than 20% increase from baseline in the sum of the diameters of all target lesions; 2) **median progression-free survival (mPFS)**, defined as the median duration prior to the development of disease progression or patient death; 3) **overall survival (OS)**, defined as time from first dose of OncoType-informed drug to death due to any cause; and 4) **safety and tolerability**, defined as the incidence of Grade 3/4 AEs in terms categorized and graded according to NCI CTCAE v4.0. We will estimate DCR, mPFS, and OS and their 95% confidence interval.

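### The tested match rate is defined by an algorithm threshold, but the 50% it is powered for is introduced as the share of subjects with validated matches

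*Combined protocol and SAP*

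**What the plan says.** - **Definition.** Section 2.1.2, like the synopsis objectives, gives the match rate as "defined as the fraction of subjects who match with at least one OncoTreat-priotitized agent", with the qualifier p < 1×10⁻⁵. PDX/PDO results are not mentioned. Section 12 restates it as a match with at least one drug, again without a validation condition.
- **Planning rate.** Section 12 says "We hypothesize that we will validate OncoTreat matches for 50% of subjects" and that 60% of matches lead to treatment. The same 50% then appears in the power statement: "we will have 97% power with alpha = 0.05 to detect a 50% match rate (15 of 30 subjects". The synopsis has the same inputs but a different power: "we will have 90% power with alpha = 0.05 to detect a 50% match rate".
- **Null.** The comparator in Section 12 is an "estimated match rate of 20% based on DNA profiling in PDA".
- **Preliminary data.** Section 3.4, Step 4, reports that an analysis of existing pancreatic tumour profiles "found at least one matching drug for 85% of patients". The threshold there is an FDR of 1×10⁻⁵, described as conservative.
- **Where validation sits.** Sections 1.1 and 4.1 describe it as a later stage: PDX or PDO experiments run after the OncoTreat analysis while the subject is on earlier treatment. Section 4.1 allows a surrogate model when the subject's own model fails or is late.

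**The concern.** The endpoint and its planning rate appear to describe two different steps. The definition counts a subject once a drug passes a computational threshold. The 50% is introduced as the share whose matches hold up in preclinical work. If the preliminary 85% carries over, the match-rate test compares a rate near 85% with 20%, and its result is close to settled before any validation experiment is done.

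What is at stake is the meaning of a positive match-rate result. A reader of the final report would take it as support for the hypothesis in Section 12, that matches are validated in half of subjects. The endpoint as worded would not measure that.

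**Working it through.** **Inputs.** N = 30, null p₀ = 0.20, alternative p₁ = 0.50 and α = 0.05 (Section 12 and synopsis); algorithm-level rate 0.85 (Section 3.4). The plan names neither the test nor its sidedness for this endpoint, so both are shown.

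**1. Rejection rule.** The smallest r with P(X ≥ r | 30, 0.20) no greater than the allowed upper tail:
- r = 10 gives 0.061, too large.
- r = 11 gives 0.0256, the one-sided 0.05 rule.
- r = 12 gives 0.0095, the two-sided 0.05 rule with 0.025 in the upper tail.

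**2. The plan's own power figures at 50%.**
- Exact, one-sided: P(X ≥ 11 | 30, 0.50) = 95.1%.
- Exact, two-sided: P(X ≥ 12 | 30, 0.50) = 90.0%. This reproduces the synopsis.
- Normal approximation, one-sided: Φ[(0.30√30 − 1.645 × 0.40)/0.50] = Φ(1.97) = 97.6%.
- Arcsine, one-sided: Φ[2(arcsin√0.50 − arcsin√0.20)√30 − 1.645] = 97.0%. This reproduces Section 12.

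Both stated powers can therefore be obtained, by different methods, and both refer to a true rate of 50%.

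**3. The test at the rate reported for the quantity as defined.** At 85% the expected count is 0.85 × 30 = 25.5 matches. The chance of failing to reject is about 2×10⁻¹⁰ with the rule of 11 and 2×10⁻⁹ with the rule of 12.

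**4. Allowing for unusable samples.** Section 4.1 requires more than 70% tumour and RIN > 6 but gives no failure rate. The loss below is an assumption. Failures count as non-matches, so the true rate is 0.85 × (1 − loss).

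| Assumed loss | Match rate | P(≥ 11) | P(≥ 12) |
|---|---|---|---|
| 0% | 85% | >99.99% | >99.99% |
| 20% | 68% | 99.99% | 99.96% |
| 30% | 59.5% | 99.7% | 99.0% |
| 40% | 51% | 96.1% | 91.8% |
| 50% | 42.5% | 79.6% | 67.5% |
| 60% | 34% | 44.6% | 30.3% |

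**5. What the definition cannot see.** Suppose, for illustration, that only 25% of subjects had a validated match. A test on validated matches would succeed with probability P(X ≥ 11 | 30, 0.25) = 10.6%, or P(X ≥ 12 | 30, 0.25) = 5.1%. The endpoint as defined would still succeed with the probabilities in the table, because validation does not enter it.

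**The case against.** **Starting treatment is the lead feasibility measure.** The synopsis and Section 12 both name it as the primary feasibility outcome, tested at 30% against 5%, and Section 12 introduces the match rate as something also assessed. A subject starts treatment only after a board recommendation informed by preclinical data, and only if the drug is available (Section 4.1). A reader might infer that feasibility could be declared on the computation alone. The documents do not support that: no rule lets the match rate by itself establish feasibility. This objection stands and limits the point to the match-rate component.

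**The 85% comes from tumours already profiled.** Part 1 depends on fresh biopsies passing quality checks, and the loss is unknown. A reader might infer that the test can hardly fail. That needs loss to stay below roughly 40–50%. At 40% the rate is 51% and the test behaves much as planned; at 60% failure is more likely than success. This also stands.

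**The wording is open to other readings.** Section 1.1 has the tumour board prioritise a treatment, so a prioritised agent might mean a board choice. The p-value qualifier, and Section 3.3, which attributes prioritising to the algorithm, favour the algorithm reading; either way the text needs an edit. Nor does Section 12 say that its 50% includes board review.

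**p-value and FDR may be used interchangeably.** An FDR cut-off is normally at least as strict as a raw p-value cut-off of the same size, so the difference gives no reason to think 85% too high for the endpoint. Putting an exact p-value on that FDR would need a drug count and a number of hits; the counts given differ (121 + 228 = 349 in Step 3, 336 in the Figure 4 legend, about 500 in Section 3.3). This supports a note on terminology only.

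**The 20% null has no stated validation condition.** An algorithm-level match is arguably closer to it. This is a real cost of the change.

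**Conclusion.** The mismatch is in the text. The match rate is defined at algorithm level, its 50% planning rate is introduced as validated matches, and the protocol's own figure for the algorithm-level quantity is 85%. On that figure the test against 20% is virtually certain to succeed. It remains likely to succeed (96% one-sided, 92% two-sided) with 40% of subjects lost to tissue or RNA failure. Below that level of loss, a positive result says little about whether matches survive validation.

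This rests on three assumptions: the 85% carries over to Part 1 subjects with a usable profile, failures count as non-matches, and the 50% means what its introducing sentence says. The start-of-treatment measure, the ORR endpoint and the sample size of 30 are not called into question by this point. The change should be made, because it is cheap and determines how a positive match-rate result can be read.

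**What to change.** Make the definition and the planning rate refer to one quantity.

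- In Sections 1, 2.1 and 12, define the tested match as a subject with at least one OncoTreat drug supported by the preclinical validation. State whether support from a surrogate model (Section 4.1) counts. Leave drug availability out, since the start-of-treatment measure already covers it.
- State that the denominator is all 30 subjects enrolled in Part 1. Section 10.2 limits the feasibility analysis to subjects who received a dose; applied to the match rate, that would push it to about 100%.
- Keep 50% against 20% for the validated match, and name the test and its sidedness. Exact power is 95% one-sided or 90% two-sided, so N does not change. Give the same figure in the synopsis and Section 12.
- Report the algorithm-level rate descriptively beside the 20% DNA-profiling rate, with the number of subjects who had no usable profile. Note that the 20% has no stated validation condition and is therefore a conservative null for a validated match.
- Use one threshold term, p-value or FDR, throughout.

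The cost is a wording amendment. The headline match rate will be lower than the algorithm-level rate, and the comparison with DNA profiling will be less like-for-like.

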2.2 Secondary Objectives & Endpoints

*Note: The secondary objects only apply for patients who are initiated on treatment with an OncoTreat-prioritized FDA-approved or early-phase investigational drug.

2.2.1 Objectives:

The secondary objectives of this study are to:

- To describe the safety and tolerability of using OncoTreat to inform rational treatment decision in subjects with advanced PDA who have progressed on one or two prior lines of therapy.
- To assess the efficacy of OncoTreat by estimating the disease control rate (DCR) at 16 and 24 weeks, the median progression-free survival (PFS), the overall survival (OS), and the CA 19-9 tumor marker response.
- To assess the pharmacokinetics of each OncoTreat-prioritized agent in subjects with advanced PDA.

2.2.2 Endpoints:

Secondary endpoints of interest include:

- Safety/tolerability
 - Incidence of Grade 3/4 adverse events (AEs) in terms categorized and graded according to the National Cancer Institute Terminology Criteria for Adverse Events (NCI CTCAE v4.0).
 - Incidence of dose modifications, interruptions, and discontinuations.
 - Note: OncoTreat-prioritized agents will be dosed at the FDA-approved dose (if available) or the recommended phase 2 dose for investigational agents. Safety endpoints as they pertain to specific drugs will not be assessed in this prospective study, as only a very small number of patients will be assigned to any one of these drugs, all of which are FDAapproved or have been studied in early phase clinical trials and have track records of safety/tolerability.
- DCR, defined as the proportion of subjects with a complete or a partial response as the best response or stable disease, according to RECIST v1.1 criteria.
- PFS, defined as the time from first dose of OncoTreat-prioritized drug to the first occurrence of disease progression or death from any cause (whichever occurs first), using RECIST v1.1 criteria.
- OS, defined as the time from first dose of OncoTreat-informed study drug to death due to any cause.
- Tumor marker response of CA 19-9, defined as ≥ 50% in CA 19-9 in relation to the baseline level at least once during the treatment period.
- Serum concentration or PK parameters for each OncoTreat-prioritized agent.
- Relationship between serum concentration or PK parameters and endpoints of interest.

